9.1.4. Confidentiality

The investigator must assure that subjects' anonymity will be strictly maintained and that their identities are protected from unauthorized parties. Only subject initials, date of birth, another unique identifier (as allowed by local law) and an identification code will be recorded on any form or biological sample submitted to the sponsor, IRB/IEC/EC, or laboratory. Laboratory specimens must be labeled in such a way as to protect subject identity while allowing the results to be recorded to the proper subject. Refer to specific laboratory instructions for further details. NOTE: The investigator must keep a Screening log showing codes, names, and addresses for all subjects screened and for all subjects enrolled in the trial. Subject data will be processed in accordance with all applicable regulations.

The investigator agrees that all information received from Gilead, including but not limited to the investigator brochure, this protocol, eCRF, the IMP, and any other study information, remain the sole and exclusive property of Gilead during the conduct of the study and thereafter. This information is not to be disclosed to any third party (except employees or agents directly involved in the conduct of the study or as required by law) without prior written consent from Gilead. The investigator further agrees to take all reasonable precautions to prevent the disclosure by any employee or agent of the study site to any third party or otherwise into the public domain.

9.1.5. Study Files and Retention of Records

The investigator must maintain adequate and accurate records to enable the conduct of the study to be fully documented and the study data to be subsequently verified. These documents should be classified into at least the following two categories: (1) investigator's study file, and (2) subject clinical source documents.

The investigator's study file will contain the protocol/amendments, CRF and query forms, IRB/IEC/EC and governmental approval with correspondence, informed consent, drug records, staff curriculum vitae and authorization forms, and other appropriate documents and correspondence.

The required source data should include sequential notes containing at least the following information for each subject:

- Subject identification (name, date of birth, gender);
- Documentation that subject meets eligibility criteria, ie, history, PE, and confirmation of diagnosis (to support inclusion and exclusion criteria);

- Documentation of the reason(s) a consented subject is not enrolled;
- Participation in study (including study number);
- Study discussed and date of informed consent;
- Dates of all visits;
- Documentation that protocol specific procedures were performed;
- Results of efficacy parameters, as required by the protocol;
- Start and end date (including dose regimen) of IMP, including dates of dispensing and return;
- Record of all adverse events and other safety parameters (start and end date, and including causality and severity);
- Concomitant medication (including start and end date, dose if relevant; dose changes);
- Date of study completion and reason for early discontinuation, if it occurs.

All clinical study documents must be retained by the investigator until at least 2 years or according to local laws, whichever is longer, after the last approval of a marketing application in an ICH region (ie, United States, Europe, or Japan) and until there are no pending or planned marketing applications in an ICH region; or, if no application is filed or if the application is not approved for such indication, until 2 years after the investigation is discontinued and regulatory authorities have been notified. Investigators may be required to retain documents longer if specified by regulatory requirements, by local regulations, or by an agreement with Gilead. The investigator must notify Gilead before destroying any clinical study records.

Should the investigator wish to assign the study records to another party or move them to another location, Gilead must be notified in advance.

If the investigator cannot provide for this archiving requirement at the study site for any or all of the documents, special arrangements must be made between the investigator and Gilead to store these records securely away from the site so that they can be returned sealed to the investigator in case of an inspection. When source documents are required for the continued care of the subject, appropriate copies should be made for storage away from the site.

9.1.6. Electronic Case Report Forms

For each subject consented, an eCRF will be completed by an authorized study staff member whose training for this function is documented according to study procedures. The eCRF should be completed in a timely manner to enable the sponsor to perform central monitoring of safety data. Subsequent to data entry, a study monitor will perform source data verification within the EDC system. Original entries as well as any changes to data fields will be stored in the audit trail of the system. Prior to database lock (or any interim time points as described in the clinical data management plan), the investigator will use his/her log in credentials to confirm that the forms have been reviewed, and that the entries accurately reflect the information in the source documents. The eCRF capture the data required per the protocol schedule of events and procedures. System-generated or manual queries will be issued to the investigative site staff as data discrepancies are identified by the monitor or internal Gilead staff, who routinely review the data for completeness, correctness, and consistency. The site coordinator is responsible for responding to the queries in a timely manner, within the system, either by confirming the data as correct or updating the original entry, and providing the reason for the update (eg, data entry error). At the conclusion of the trial, Gilead will provide the site with a read-only archive copy of the data entered by that site. This archive must be stored in accordance with the records retention requirements outlined in Section 9.1.5.

9.1.7. Investigational Medicinal Product Accountability and Return

The investigator or designee (ie, pharmacist) is responsible for ensuring adequate accountability of all used and unused study drug. This includes acknowledgment of receipt of each shipment of study product (quantity and condition), subject dispensing records, and returned or destroyed study product. Dispensing records will document quantities received from Gilead Sciences and quantities dispensed to subjects, including lot number, date dispensed, subject identifier number, subject initials, and the initials of the person dispensing the medication.

At study initiation, the monitor will evaluate the site's standard operating procedure of investigational medicinal product/destruction in order to ensure that it complies with Gilead Sciences requirements. Drug may be returned or destroyed on an ongoing basis during the study, if appropriate. At the end of the study, following final drug inventory reconciliation by the monitor, the study site will dispose of and/or destroy all unused investigational medicinal product supplies, including empty containers, according to these procedures. If the site cannot meet Gilead Science's requirements for disposal, arrangements will be made between the site and Gilead Sciences or its representative for destruction or return of unused investigational medicinal product supplies.

All drug supplies and associated documentation will be periodically reviewed and verified by the study monitor over the course of the study.

9.1.8. Inspections

The investigator should understand that source documents for this trial should be made available to appropriately qualified personnel from Gilead Sciences and its representatives, to IRBs/IECs/ECs, or to regulatory authority or health authority inspectors.

9.1.9. Protocol Compliance

The investigator is responsible for ensuring the study is conducted in accordance with the procedures and evaluations described in this protocol.

9.2. Sponsor Responsibilities

9.2.1. Protocol Modifications

Protocol modifications, except those intended to reduce immediate risk to study subjects, may be made only by Gilead. The investigator must submit all protocol modifications to the IRB/IEC/EC in accordance with local requirements and receive documented approval before modifications can be implemented.

9.2.2. Study Report and Publications

A clinical study report (CSR) will be prepared and provided to the regulatory agency. Gilead will ensure that the report meets the standards set out in the ICH Guideline for Structure and Content of Clinical Study Reports (ICH E3). Note that an abbreviated report may be prepared in certain cases.

Investigators in this study may communicate, orally present, or publish in scientific journals or other scholarly media only after the following conditions have been met:

- The results of the study in their entirety have been publicly disclosed by or with the consent of Gilead in an abstract, manuscript, or presentation form; or
- The study has been completed at all study sites for at least 2 years

No such communication, presentation, or publication will include Gilead's confidential information (see Section 9.1.4).

The investigator will submit to Gilead any proposed publication or presentation along with the respective scientific journal or presentation forum at least 30 days before submission of the publication or presentation. The investigator will comply with Gilead's request to delete references to its confidential information (other than the study results) in any paper or presentation and agrees to withhold publication or presentation for an additional 60 days in order to obtain patent protection if deemed necessary.

9.3. Joint Investigator/Sponsor Responsibilities

9.3.1. Payment Reporting

Investigators and their study staff may be asked to provide services performed under this protocol, eg, attendance at Investigator's Meetings. If required under the applicable statutory and regulatory requirements, Gilead will capture and disclose to Federal and State agencies any expenses paid or reimbursed for such services, including any clinical trial payments, meal, travel expenses or reimbursements, consulting fees, and any other transfer of value.

9.3.2. Access to Information for Monitoring

In accordance with regulations and guidelines, the study monitor must have direct access to the investigator's source documentation in order to verify the accuracy of the data recorded in the eCRF.

The monitor is responsible for routine review of the eCRF at regular intervals throughout the study to verify adherence to the protocol and the completeness, consistency, and accuracy of the data being entered on them. The monitor should have access to any subject records (including electronic medical records, if applicable) needed to verify the entries on the eCRF. The investigator agrees to cooperate with the monitor to ensure that any problems detected through any type of monitoring (central, on site) are resolved.

9.3.3. Monitoring and Oversight of Biomarker Specimens

Biomarker research specimens will be tracked in a manner consistent with Good Clinical Practice by a quality-controlled, auditable, and appropriately validated laboratory information management system, to ensure compliance with data confidentiality as well as adherence to authorized use of specimens as specified in this protocol and in the Informed Consent Form.

9.3.4. Access to Information for Auditing or Inspections

Representatives of regulatory authorities or of Gilead may conduct inspections or audits of the clinical study. If the investigator is notified of an inspection by a regulatory authority the investigator agrees to notify the Gilead medical monitor immediately. The investigator agrees to provide to representatives of a regulatory agency or Gilead access to records, facilities, and personnel for the effective conduct of any inspection or audit.

9.3.5. Study Discontinuation

Both the sponsor and the investigator reserve the right to terminate the study at any time. Should this be necessary, both parties will arrange discontinuation procedures and notify the appropriate regulatory authority (ies), IRBs, IECs, and ECs. In terminating the study, Gilead and the investigator will assure that adequate consideration is given to the protection of the subjects' interests.

Appendix 2. Study Procedures Table

	Screen	ing ^a					Trea	tment ^b					-		Post	Treatmen	ıt			Unscheduled Visit	
			Pas	eline/		/eek 1	V	veek 2		v eek 3		eek 4/ CoT ^t	Week 6	Week 8 ^u	Week 12 ^u	Week 16	Week 20	Week 24 ^u	Follow Up visit ^v		
	-14 da	ays	1255-127 B	ay 1					±3 da	ays							±5 days				
Informed Consent	x																				
Review Inclusion/Exclusion Criteria	X		2	x		X															
Medical History	x		î.						2		3					. 3					
AUDIT / SADQ ^c	x																				
QoL (CLDQ) c			2	х	2							x					i .	X	2	-	
Alcohol Consumption	X		Î S	X		X		х		X		X	X	X	X	x	X	X			
Complete Physical Exam ^d	X		8	X		х		х		x		X	x	x	x	x	x	X			
Height	x		5		2				e.				¢ 8					55	2	4	
Weight	X		1 8	X	3		2				2	X	6		X	. 3		Х	8		
Vital Signs	X		3	X		x		X		x		x	x	X	x	x	X	х			
12-lead ECG ^e	X			x	5					1		x		X					5		
	Local lab	Central lab	Local lab	Central lab	Local lab	Central lab	Local lab	Central lab	Local lab	Central lab	Local lab	Central lab									
Urine Drug Screen ^f	X	x			- 2. 	G				s											
Urinalysis ^g	x		5	5		3						2						4			
HRS ^e	X		6	х	3	X		X		х		X	X	X	x	x	x	X	x	x	
Infection ^e	x			x	0	x		x		х		x	x	x	x	x	x	x	x	X	
Hematology	x	х	5	x	2	X		х		X		X	X	х	X	x	X	x	X	X	
Chemistry ⁱ	x	x	x	x	x	X	x	x	x	x	x	X	x	x	x	X	X	x	x	x	

GS-4997 Protocol GS-US-416-2124 Gilead Sciences, Inc.

	Scre	ening ^a			154		Trea	tment ^b	3		6.4				Post	Treatmen	at	1.9		Unschedule Visit	
			D	seline/	V	Veek 1		Veek 2	V	Veek 3		eek 4/ EoT ^t	Week 6	Week 8"	Week 12 ^u	Week 16	Week 20	Week 24 ^u	Follow Up visit ^v		
	-14	days		ay 1	3				±3 d	ays				±5 days						-	
Hepatitis B and C, HIV ^j	X	X																			
Coagulation Tests ^k	X	X	X	x		X		x		X		x	x	x	X	x	x	x	X	X	
Pregnancy Test ¹	X (urine)	X (serum)		X								X		X	X	X	X	X			
	Local Lab	Central Lab	Local Lab	Central Lab	Local Lab	Central Lab	Local Lab	Central Lab	Local Lab	Central Lab	Local Lab	Central Lab									
Blood Cultures	x	-			~												-		1		
Ascitic Fluid Tap ^m	X																				
Liver Biopsy	X ⁿ			8	ĺ.				a 10			c.									
Insulin		X		x								x			X			x			
Lipid Profile		х		x								x			x			x			
Blood Sample for Biomarkers°		x	0 5	x	8	X		x	2			x		X	x			X			
Urine Sample for Biomarkers			6	x	3				2			х						X	8 9 5		
ELF test, LOXL2				x								x			X		-	X	c		
Hemoglobin A1c				x											x			x			
Hepatic Encephalopathy ^d		x	1		Ĩ.	x		x		x		x	x	X	x	x	x	x	x	x	
Ascites ^d	13	X ^h	6			X		x		x		X	x	x	x	x	x	x	X	x	
Chest X-ray		X			8		3		9 24		× .							2			
Liver Ultrasound		x	2		8				8		3										
Review Concomitant Medications		x	ŝ	X		X		X		X		X	x	x	X	X	X	x	X	X	

GS-4997 Protocol GS-US-416-2124 Gilead Sciences, Inc.

	Screening ^a			Treatment ^b					Post	Treatme	nt			Unscheduled Visit	
		Baseline/	Week 1	Week 2	Week 3	Week 4/ EoT ^t	Week 6	Week 8 ^u	Week 12 ^u	Week 16	Week 20	Week 24 ^u	Follow Up visit ^v		
	-14 days	Day 1			±3 days						±5 days				
Adverse Events	X	Х	Х	X	Х	X	X	Х	X	Х	X	X	X	x	
Sparse PK Sample ^p		Х	Х	X		X ^p									
Stool Collection		Х				X						X			
Randomization ^q		X			2			-				-			
GS-4997 Dispensing		Х													
Prednisolone Dispensing		X	X	E E	X						3				
PPD															
Genomic Sample ^s		Х				-		-					-		
Study Drug Adherence			Х	X	х	X									
FibroScan ^w		X				X						X			
Lille Score ^x			Х	X	Х	X									

a The visit window may be extended under special circumstances with explicit approval of the Medical Monitor. Subjects who fail to meet eligibility criteria due to an abnormal laboratory result may undergo re-testing of the abnormal analyte once during the Screening window. This will be done at the discretion of the investigator and also with prior approval of the Medical Monitor. The following laboratory tests will be collected at Screening for testing at both the local and central laboratories: urine drug screen, hematology, chemistry, and coagulation tests. Eligibility will be based on local laboratory results. For urine drug screen, local laboratory testing done within 10 days of the Screening visit may be used to determine eligibility. For hepatitis B serology, hepatitis C serology, and HIV serology, these tests will be sent to both the local and central laboratory and be the basis for eligibility. A serum pregnancy test will be sent only to the central laboratory at Screening.

b During the hospitalization period, subjects will be evaluated daily with assessments to include a review of adverse events, concomitant medications, study drug adherence, and a symptom-directed PE including assessments for ascites and HE. Findings based on these assessments and laboratory investigations obtained by treating physicians as part of routine care will be assessed by the investigator for triggers that may necessitate further evaluation and/or treatment discontinuation and managed accordingly per Section 7 of the protocol.

c A Legally Authorized Representative may assist the subject in completing the questionnaires. If the subject is unable or refuses to complete a questionnaire, this should be documented on the relevant eCRF.

- d Perform a complete Physical Exam with a focus on ascites and encephalopathy.
- e Please see Section 6.9 for description of assessments and record diagnosis/abnormal findings as an AE.

f Drug screen for amphetamines, cocaine and opiates (ie heroin, morphine).

- g Urinalysis (routine and microscopic) and culture to be performed by local lab.
- h Subjects with evidence of sepsis or gastrointestinal bleeding may be treated for a minimum of 2 days with appropriate antibiotics. Once deemed stable, subject may continue Screening and randomized if eligible.
- i Chemistry will include: alanine aminotransferase (ALT), aspartate aminotransferase (AST), albumin, alkaline phosphatase, bicarbonate, blood urea nitrogen, calcium, chloride, creatinine, glucose, lactate dehydrogenase (LDH), magnesium, phosphorus, potassium, sodium, total and direct bilirubin, total protein, uric acid, gamma-glutamyl transferase (GGT). Chemistry must be collected for both local and central lab at Baseline/Day1, Week 1, Week 2, Week 3, and Week 4 for Lille Score
- j Local laboratory results for Hepatitis B and C and HIV Serology done within 10 days of the Screening visit may be used to determine eligibility.
- k Coagulation Panel includes: PT, PTT and INR. Coagulation must be collected for both local and central lab at Baseline/Day visit for Lille Score.
- 1 Females of childbearing potential only. Serum pregnancy test at Screening done at central lab. Urine pregnancy test at Screening and other visits.
- m Paracentesis with ascitic fluid cell count, differential, and culture will be performed if clinically-detectable ascites is present.
- n Liver biopsy obtained during the current hospital admission prior to Screening is acceptable. Liver biopsy can be performed up to 7 days post Baseline/Day 1. However, if biopsy results are not consistent with AH, the subject will discontinue study drug within 3 days of receipt of liver biopsy result, attend an EoT visit as soon as possible and attend a 30-day FU visits and be withdrawn from the study. If the liver biopsy sample is inadequate for a pathologic diagnosis of AH, but does not reveal an alternative etiology, the subject may remain in the study.
- o Blood for Biomarkers collection will occur at all study sites. Biomarker phospho-p38 blood sample will be collected prior to the first dose of study drug only at US study sites.
- p Please refer to Section 6.4.1 for sample collection instructions. If subject's last dose of study drug is prior to the Week 4 visit, PK sample can still be collected at Week 4 as long as last dose date and time is prior to sample collection. If a subject requires hemodialysis/hemoperfusion/peritoneal dialysis therapy, please refer to Section 6.4.1 for collection instructions.
- q Stratification of MELD < or ≥ 25 at Screening will be based on local laboratory testing and utilize the following calculator: http://www.mdcalc.com/original-meld-score-pre-2016-model-for-end-stage-liver-disease
- r PPD

s PPD

- t Subjects discontinuing treatment at any time prior to Week 4 for any reason should complete the procedures required for the Week 4 / End of Treatment Visit. These subjects will require a phone contact between study days 28-35 to assess for mortality and liver transplantation and have a follow up visit 30 days after their last dose of study drug, prior to being withdrawn from the study.
- u Subjects with a Week 8, Week 12, or Week 24 visit prior to Day 56, Day 84, or Day 168 respectively will be required to have a telephone contact between Days 56-63, Days 84-89, or 168-173 respectively to assess for mortality and liver transplantation.
- v Subjects whose liver biopsy results are not consistent with AH or whose HIV or hepatitis B or C serologies from the central laboratory are positive, must stop study drug within 3 days of receipt of results. Subjects whose serum pregnancy testing from the central laboratory is positive at Screening must stop study drug immediately upon receipt of this result. All subjects stopping study drug for these reasons should attend an EoT visit as soon as possible and have a follow up visit 30 days after their last dose of study drug, prior to being withdrawn from the study. If the liver biopsy sample is inadequate for a pathologic diagnosis of AH, but does not reveal an alternative etiology, the subject may remain in the study.
- w At sites where available and only on subjects without ascites.
- x Sites to calculate based on local laboratory results using the following calculator: http://www.mdcalc.com/lille-model-alcoholic-hepatitis/. When using the calculator, ensure the Day 7 total bilirubin is changed to Weeks 2, 3, and 4 values at the appropriate time points.

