Subjects whose liver biopsy results are not consistent with AH or whose HIV or hepatitis B or C serologies from the central laboratory are positive must stop study drug within 3 days of receipt of results. In subjects in whom a liver biopsy is insufficient to confirm a diagnosis of AH, subjects may remain in the study if no alternative diagnosis is suggested on biopsy. Subjects whose serum pregnancy testing from the central laboratory is positive at Screening must stop study drug immediately upon receipt of this result. All subjects stopping study drug for inconsistent liver biopsy results, for positive HIV or hepatitis B or C serologies from the central laboratory, or for positive serum pregnancy testing from the central laboratory should attend an EoT visit as soon as possible and have a follow up visit 30 days after their last dose of study drug, prior to being withdrawn from the study (see Sections 6.7 and 6.8 of this protocol for clarification on study drug vs. study discontinuation).

Intensive PK Sub-study

[figure not shown]

Table 3-1. Because biomarker science is a rapidly evolving area of investigation, and adverse events in particular are difficult to predict, it is not possible to specify prospectively all tests that will be done on the specimens provided. The testing outlined is based upon the current state of scientific knowledge. It may be modified during or after the end of the study to remove tests no

longer indicated and/or to add new tests based upon the growing state of the art knowledge. If a test will no longer be performed because the assay is not robust, sample collection may also be withdrawn to reduce burden on subjects.

Specimens will be collected from all subjects. Samples will be destroyed no later than 15 years after the end of the study. The specimen storage period will be in accordance with the IRB/IEC/EC-approved Informed Consent Form (ICF) and applicable laws (eg, health requirements).

Biomarker Focus	Planned Biomarkers	Rational	Specimen Collected
Liver tissue surrogate marker panel	ELF Test	Assess potential changes in liver fibrosis due to treatment	Blood
Liver tissue damage marker	Serum LOXL2	Assess potential changes in liver tissue damage due to treatment	Blood
Apoptosis and Necrosis markers	Circulating Cytokeratin 18 (CK18) fragments, M30 for apoptosis and M65 for all dying cells)	Determine changes in liver cell death due to treatment	Blood

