5.1.1. Procedures for Breaking Treatment Codes

In the event of a medical emergency where breaking the blind is required to provide medical care to the subject, the investigator may obtain treatment assignment directly from the IWRS system for that subject. Gilead recommends but does not require that the investigator contacts the Gilead medical monitor before breaking the blind. Treatment assignment should remain blinded unless that knowledge is necessary to determine subject emergency medical care. The rationale for unblinding must be clearly explained in source documentation and on the electronic case report form (eCRF), along with the date on which the treatment assignment was obtained. The investigator is requested to contact the Gilead medical monitor promptly in case of any treatment unblinding.

Blinding of study treatment is critical to the integrity of this clinical trial and therefore, if a subject's treatment assignment is disclosed to the investigator, the subject will have study treatment discontinued. All subjects will be followed until study completion unless consent to do so is specifically withdrawn by the subject.

Gilead Drug Safety and Public Health (DSPH) may independently unblind cases for expedited reporting of suspected unexpected serious adverse reactions (SUSARs).

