6.3.5. Follow Up Visit (±5 Days)

Subjects should return for a Follow-Up Visit 30 days after their last dose of study drug.

Subjects whose liver biopsy results are not consistent with AH or whose HIV or hepatitis B or C serologies from the central laboratory are positive, must stop study drug within 3 days of receipt of results. If the liver biopsy sample is inadequate for pathologic diagnosis of AH and no alternative diagnosis is suggested on biopsy, then the subject may remain in the study. Subjects whose serum pregnancy testing from the central laboratory is positive at Screening must stop study drug immediately upon receipt of this result. All subjects stopping study drug for these reasons should attend an EoT visit as soon as possible and have a follow up visit 30 days after their last dose of study drug, prior to being withdrawn from the study. Subjects discontinuing both study drugs prior to Week 2 should complete an end of treatment visit after stopping drug, a 30-day safety FU visit, and all post-treatment follow-up visits. Subjects discontinued after Week 2 should complete an end of treatment assessments as outlined in Appendix 2.

- Record all concomitant medications that the subject has taken since the previous visit
- Record any SAEs and all adverse events occurring since the previous visit
- Assessments for HE, ascites, HRS and infection

- Obtain blood samples for:
 - Hematology
 - Chemistry: ALT, AST, albumin, alkaline phosphatase, bicarbonate, BUN, calcium, chloride, creatinine, glucose, LDH, magnesium, phosphorus, potassium, sodium, total and direct bilirubin, total protein, uric acid, GGT

- Coagulation Tests: PT, PTT, and INR

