6.7. Assessments for Premature Discontinuation from Study

Discontinuation from study drug dosing and discontinuation from the study (including follow-up visits and phone contact at Week 8, Week 12, and Week 24) are 2 distinct actions.

Subjects with histologically confirmed AH who discontinue study drug (for any reason other than death) prior to completion of the assigned dosing period, should complete an EoT visit, a 30 day follow up visit, and all required follow-up study visits.

Subjects whose liver biopsy results are not consistent with AH or whose HIV or hepatitis B or C serologies from the central laboratory are positive, must stop study drug within 3 days of receipt of results. Subjects whose serum pregnancy testing from the central laboratory is positive at Screening must stop study drug immediately upon receipt of this result. All subjects stopping study drug for these reasons should attend an EoT visit as soon as possible and have a follow up visit 30 days after their last dose of study drug, prior to being withdrawn from the study. These subjects will not complete the remaining follow-up study visits.

Subjects are considered to have completed the study after the Follow up Week 24 visit, regardless of treatment duration and/or early termination from study drug.

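### Appendix 2 footnote t withdraws early stoppers after a 30-day visit, whereas protocol Section 6.7 keeps those with confirmed AH in follow-up to Week 24

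*Protocol*

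**What the plan says.** Footnote t, attached to the Week 4/EoT column of Appendix 2, opens with "Subjects discontinuing treatment at any time prior to Week 4 for any reason". These subjects have the end-of-treatment procedures, a phone contact on Study Days 28 to 35 to check for death or "liver transplantation and have a follow up visit 30 days after their last dose of study drug, prior to being withdrawn from the study".

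Protocol Section 6.7 gives a different rule. It covers "Subjects with histologically confirmed AH who discontinue study drug (for any reason other than death) prior to completion of the assigned dosing period". According to that section, they "should complete an EoT visit, a 30 day follow up visit, and all required follow-up study visits". It adds: "Subjects are considered to have completed the study after the Follow up Week 24 visit, regardless of treatment duration and/or early termination from study drug". It also treats stopping drug and leaving the study as separate actions. Its only early exits are a biopsy not consistent with AH, a positive central HIV, hepatitis B or hepatitis C serology, and a positive central serum pregnancy test. Footnote v covers those same exits separately.

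Other sections side with Section 6.7:

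- Section 3.2, on the biopsy, serology and pregnancy stops, tells the reader to "see Sections 6.7 and 6.8 of this protocol for clarification on study drug vs. study discontinuation".
- Section 5.1.1, on subjects taken off treatment after unblinding to the investigator: "All subjects will be followed until study completion unless consent to do so is specifically withdrawn by the subject".
- Section 6.3.5 (and Section 3.2 in the same terms) asks those who stop both drugs before Week 2 for an end-of-treatment visit, "a 30-day safety FU visit, and all post-treatment follow-up visits".
- Section 6.3.4 sends subjects who meet discontinuation criteria to post-treatment visits, again by reference to Appendix 2.
- SAP Section 1.2 plans 24 weeks of follow-up and excepts only alternative-etiology biopsies and positive serologies.

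**The concern.** Two current instructions give opposite answers for the same subject: a confirmed-AH subject who stops before Week 4 because of, for example, an adverse event, a Lille score above 0.85 or personal choice. Such subjects belong to the Full Analysis Set, the primary efficacy set. For stops after Week 2, the sentences in Sections 3.2 and 6.3.5 mention only end-of-treatment assessments as laid out in Appendix 2, and footnote t is what a site finds there.

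At stake are the secondary outcomes at Weeks 8, 12 and 24, chiefly mortality, transplantation and transplant-free survival. Some early stops follow prognosis (a Lille score above 0.85 is one trigger), so censoring at exit could be informative.

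**Working it through.** **1. The rules side by side**

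| Place | Who | After stopping |
|---|---|---|
| Appendix 2, footnote t | Any stop before Week 4 | EoT procedures, call on Days 28–35, 30-day visit, withdrawn |
| Protocol 6.7 | Confirmed AH, any reason except death | EoT, 30-day visit, all remaining visits; complete at Week 24 |
| Protocol 3.2, 6.3.5 | Both drugs stopped before Week 2 | EoT, 30-day visit, all post-treatment visits |
| Protocol 3.2, 6.3.5 | Stopped after Week 2 | EoT assessments per Appendix 2; nothing further stated |
| Protocol 6.3.4 | Discontinuation criteria met, all drugs stopped | EoT, then post-treatment visits per Appendix 2 |
| Protocol 5.1.1 | Stopped after unblinding | Followed to study completion |
| SAP 1.2 | All, except alternative-etiology biopsy or positive serology | 24 weeks |
| Protocol 6.7, footnote v | Biopsy not AH, positive central serology or pregnancy test | 30-day visit, then withdrawn |

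Footnote t agrees with Section 6.7 only in the last row. Because footnote v already covers that row and footnote t has no carve-out, footnote t cannot be read as meaning that group alone.

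**2. When follow-up ends under footnote t**

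Inputs: last dose on Day L, 1 to 27; visit 30 days later; window ±5 days (Section 6.3.5). Nominal exit = L + 30; latest exit = L + 35.

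| L | Nominal exit | Latest exit |
|---|---|---|
| 1 | 31 | 36 |
| 14 | 44 | 49 |
| 20 | 50 | 55 |
| 21 | 51 | 56 |
| 25 | 55 | 60 |
| 26 | 56 | 61 |
| 27 | 57 | 62 |

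- Day 56 (Week 8) is reached nominally only for L = 26 or 27, and at the end of the window for L = 21 to 27. Among stops on Days 15 to 27 that is 2 of 13 and 7 of 13 stop days.
- Day 84 and Day 168 are never reached: the latest exit, Day 62, is 84 − 62 = 22 and 168 − 62 = 106 days short.

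**3. What the SAP then does**

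- Deaths (SAP 6.2.1): the denominator is those who died or are known alive through the timepoint, and Weeks 8, 12 and 24 follow the Day 28 rule. Survivors at exit drop out unless status is obtained later.
- Transplant (SAP 6.2.2): the denominator is those transplanted or known to be still on study. Read strictly, withdrawn subjects drop out even if their status is known.
- Kaplan-Meier (SAP 6.2.1, 6.2.3): subjects are censored at the last known date, which may come from a survival status form.

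**4. Illustration of direction (assumed rates only)**

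The documents give no stopping rate. Let s be the share exiting, mS their Week 24 mortality, fS the share of their deaths before exit, and mO the mortality of the others, half of it before exit. No status is collected after exit.

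- True = s·mS + (1−s)·mO
- Crude = [s·mS·fS + (1−s)·mO] / [1 − s(1 − mS·fS)]
- KM = 1 − [1 − (s·mS·fS + (1−s)·mO/2)]·(1−mO)/(1−mO/2)

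Case A: s = 0.20, mS = 0.50, fS = 0.25, mO = 0.15. True = 0.10 + 0.12 = 22.0%. Crude = 0.145/0.825 = 17.6% (−4.4 points). KM = 1 − 0.915 × 0.85/0.925 = 15.9% (−6.1 points).

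Case B: s = 0.20, mS = mO = 0.30, fS = 0.75. True = 30.0%. Crude = 0.285/0.845 = 33.7% (+3.7 points). KM = 1 − 0.835 × 0.70/0.85 = 31.2% (+1.2 points).

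The error can go either way. With survival status collected from everyone who exits, it is 0 for mortality.

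**The case against.** The best defence is that one footnote clause stands against Sections 5.1.1, 6.3.4 and 6.7 and SAP 1.2, and that Section 3.2 names Section 6.7 as the place that settles drug versus study discontinuation. Section 6.3.4 has no Week 2 cut-off on post-treatment visits, which narrows the gap for later stops. It also ties the end-of-treatment visit to stopping all study drugs, which largely answers whether footnote t means one drug or both. The SAP reports subjects not followed to each timepoint by reason for leaving (6.2.1, 6.2.2) and tabulates study discontinuation (4.1), so losses would be visible. The primary endpoint is safety, and the mortality test is exploratory. SAP Section 2.3 puts the last Week 8 visit at 16 February 2018. With exits no later than Day 62, nearly all would by then have happened.

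Much of this stands: the intended rule can be found, and the damage is limited and visible. It does not remove the conflict. Section 6.3.4 itself sends the site to Appendix 2, where the footnote says withdraw. Tabulating losses does not recover the outcomes.

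A reader might go further and infer that the trial withdraws its early stoppers and that its Week 24 mortality is therefore biased. The documents do not show that. They do not say how many subjects stopped, how many sites followed the footnote, or whether the survival status form was completed after exit. Nor do Section 6.7 and SAP 1.2 keep every early stopper to Week 24, since the biopsy and serology groups leave under both and the pregnancy group under Section 6.7.

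**Conclusion.** Wrong as written: an internal contradiction that should be fixed. For confirmed-AH subjects who stop before Week 4, footnote t and Section 6.7 cannot both be followed.

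What rests on the documents alone is the timing. Under footnote t, exit falls on Day 31 to 57 nominally and Day 62 at the latest, so Weeks 12 and 24 are always lost and Week 8 is lost except after the latest stops. The 30-day safety window, Day 28 status and deaths before exit are kept.

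The size of any effect on the results is unknown. For mortality it could be zero, because SAP Section 1 mentions a Week 24 subject status form and SAP 6.2.1 and 6.2.3 use survival status dates; nothing says these are collected from subjects withdrawn under footnote t. For transplantation, status after exit helps only if the denominator wording is read loosely, although transplants are recorded on the survival status form. The figures in Cases A and B rest on assumed rates. They show only that neither the direction nor the size can be taken as known.

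**What to change.** - Reconcile footnote t, and the sentences on stops after Week 2 in Sections 3.2 and 6.3.5, with Section 6.7, so that only the footnote v group leaves after the 30-day visit. State in footnote t whether one drug or both is meant.
- State in the SAP that survival and transplant status obtained after early exit counts in the denominators of 6.2.1 and 6.2.2.
- Where exits under footnote t have already happened, collect survival and transplant status at Weeks 8, 12 and 24 where consent allows, and report by arm how many subjects were withdrawn this way.
- Minor alignments at the same time: add the positive central pregnancy test to the exceptions in SAP 1.2, and use one set of call windows (footnote u has Days 84–89 and 168–173; Section 6.5.3 has Days 84–91 and 168–175).

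Cost: a wording amendment needing ethics approval (Section 9.2.1), a short SAP edit and some status calls. No treatment or stopping rule changes. If enrolment and exits are over, the SAP edit, the status collection and the count by arm are the parts that still help.
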